2.1. Assessment of overall tumor burden and measurable disease

To assess objective response or future progression, it is necessary to estimate the overall tumor burden at baseline and use this as a comparator for subsequent measurements. Only subjects with measurable disease at baseline should be included. Measurable disease is defined by the presence of at least one measurable lesion (as detailed above in Section 3).

2.2. Baseline documentation of 'target' and 'non-target' lesions

When more than one measurable lesion is present at baseline all lesions up to a maximum of five lesions total (and a maximum of two lesions per organ) representative of all involved organs should be identified as target lesions and will be recorded and measured at baseline (this means in instances where subjects have only 1 or 2 organ sites involved a maximum of 2 and 4 lesions respectively will be recorded).

Target lesions should be selected on the basis of their size (lesions with the longest diameter), be representative of all involved organs, but in addition should be those that lend themselves to reproducible repeated measurements. It may be the case that, on occasion, the largest lesion does not lend itself to reproducible measurement in which circumstance the next largest lesion which can be measured reproducibly should be selected.

Lymph nodes merit special mention since they are normal anatomical structures which may be visible by imaging even if not involved by tumor. As noted in Section 3, pathological nodes which are defined as measurable and may be identified as target lesions must meet the criterion of a short axis of ≥ 15 mm by CT scan. Only the short axis of these nodes will contribute to the baseline sum. The short axis of the node is the diameter normally used by radiologists to judge if a node is involved by solid tumor. Nodal size is normally reported as two dimensions in the plane in which the image is obtained (for CT scan this is almost always the axial plane; for MRI the plane of acquisition may be axial, sagittal or coronal). The smaller of these measures is the short axis. For example, an abdominal node which is reported as being 20 mm \times 30 mm has a short axis of 20 mm and qualifies as a malignant, measurable node. In this example, 20 mm should be recorded as the node measurement. All other pathological nodes (those with short axis ≥ 10 mm but < 15 mm) should be considered non-target lesions. Nodes that have a short axis < 10 mm are considered non-pathological and should not be recorded or followed.

A sum of the diameters (longest for non-nodal lesions, short axis for nodal lesions) for all target lesions will be calculated and reported as the baseline sum diameters. If lymph nodes are to be included in the sum, then as noted above, only the short axis is added into the sum. The baseline sum diameters will be used as reference to further characterize any objective tumor regression in the measurable dimension of the disease.

All other lesions (or sites of disease) including pathological lymph nodes should be identified as non-target lesions and should also be recorded at baseline. Measurements are not required, and these lesions should be followed as 'present', 'absent', or in rare cases 'unequivocal progression' (more details to follow). In addition, it is possible to record multiple non-target lesions involving the same organ as a single item on the case record form (eg, 'multiple enlarged pelvic lymph nodes' or 'multiple liver metastases').

2.3. Response criteria

This section provides the definitions of the criteria used to determine objective tumor response for target lesions.

2.3.1. Evaluation of target lesions

Complete Response (CR): Disappearance of all target lesions. Any pathological lymph nodes (whether target or non-target) must have reduction in short axis to < 10 mm.

Partial Response (PR): At least a 30% decrease in the sum of diameters of target lesions, taking as reference the baseline sum diameters.

Progressive Disease (PD): At least a 20% increase in the sum of diameters of target lesions, taking as reference the smallest sum on study (this includes the baseline sum if that is the smallest on study). In addition to the relative increase of 20%, the sum must also demonstrate an absolute increase of at least 5 mm. (Note: the appearance of one or more new lesions is also considered progression).

Stable Disease (SD): Neither sufficient shrinkage to qualify for PR nor sufficient increase to qualify for PD, taking as reference the smallest sum diameters while on study.

2.3.2. Special notes on the assessment of target lesions

Lymph nodes

Lymph nodes identified as target lesions should always have the actual short axis measurement recorded (measured in the same anatomical plane as the baseline examination), even if the nodes regress to below 10 mm on study. This means that when lymph nodes are included as target lesions, the 'sum' of lesions may not be zero even if complete response criteria are met, since a normal lymph node is defined as having a short axis of < 10 mm. Case report forms or other data collection methods may therefore be designed to have target nodal lesions recorded in a separate section where, in order to qualify for CR, each node must achieve a short axis < 10 mm. For PR, SD and PD, the actual short axis measurement of the nodes is to be included in the sum of target lesions.

Target lesions that become 'too small to measure'

While on study, all lesions (nodal and non-nodal) recorded at baseline should have their actual measurements recorded at each subsequent evaluation, even when very small (eg, 2 mm). However, sometimes lesions or lymph nodes which are recorded as target lesions at baseline become so faint on CT scan that the radiologist may not feel comfortable assigning an exact measure and may report them as being "too small to measure." When this occurs, it is important that a value be recorded on the case report form. If it is the opinion of the radiologist

that the lesion has likely disappeared, the measurement should be recorded as 0 mm. If the lesion is believed to be present and is faintly seen but too small to measure, a default value of 5 mm should be assigned (Note: It is less likely that this rule will be used for lymph nodes since they usually have a definable size when normal and are frequently surrounded by fat such as in the retroperitoneum; however, if a lymph node is believed to be present and is faintly seen but too small to measure, a default value of 5 mm should be assigned in this circumstance as well). This default value is derived from the 5 mm CT slice thickness (but should not be changed with varying CT slice thickness). The measurement of these lesions is potentially non-reproducible, therefore providing this default value will prevent false responses or progressions based upon measurement error. To reiterate, however, if the radiologist is able to provide an actual measure, that should be recorded, even if it is below 5 mm.

Lesions that split or coalesce on treatment

When non-nodal lesions 'fragment', the longest diameters of the fragmented portions should be added together to calculate the target lesion sum. Similarly, as lesions coalesce, a plane between them may be maintained that would aid in obtaining maximal diameter measurements of each individual lesion. If the lesions have truly coalesced such that they are no longer separable, the vector of the longest diameter in this instance should be the maximal longest diameter for the 'coalesced lesion'.

2.3.3. Evaluation of non-target lesions

This section provides the definitions of the criteria used to determine the tumor response for the group of non-target lesions. While some non-target lesions may actually be measurable, they need not be measured and instead should be assessed only qualitatively at the time points specified in the protocol.

Complete Response (CR): Disappearance of all non-target lesions and normalization of tumor marker level. All lymph nodes must be non-pathological in size (< 10 mm short axis).

Non-CR/Non-PD: Persistence of one or more non-target lesion(s) and/or maintenance of tumor marker level above the normal limits.

Progressive Disease (PD): Unequivocal progression (see comments below) of existing non-target lesions. (Note: the appearance of one or more new lesions is also considered progression).

2.3.4 New lesions

The appearance of new malignant lesions denotes disease progression; therefore, some comments on detection of new lesions are important. There are no specific criteria for the identification of new radiographic lesions; however, the finding of a new lesion should be unequivocal: ie, not attributable to differences in scanning technique, change in imaging modality or findings thought to represent something other than tumor (for example, some 'new' bone lesions may be simply healing or flare of pre-existing lesions). This is particularly important when the subject's baseline lesions show partial or complete response. For example, necrosis of a liver lesion may be reported on a CT scan report as a 'new' cystic lesion, which it is not.

A lesion identified on a follow-up study in an anatomical location that was not scanned at baseline is considered a new lesion and will indicate disease progression. An example of this is the subject who has visceral disease at baseline and while on study has a CT or MRI brain ordered which reveals metastases. The subject's brain metastases are considered to be evidence of PD even if he/she did not have brain imaging at baseline.

If a new lesion is equivocal, for example because of its small size, continued therapy and follow-up evaluation will clarify if it represents truly new disease. If repeat scans confirm there is definitely a new lesion, then progression should be declared using the date of the initial scan.

While FDG-PET response assessments need additional study, it is sometimes reasonable to incorporate the use of FDG-PET scanning to complement CT scanning in assessment of progression (particularly possible 'new' disease).

New lesions on the basis of FDG-PET imaging can be identified according to the following algorithm:

- a. Negative FDG-PET at baseline, with a positive FDG-PET at follow-up is a sign of PD based on a new lesion.
- b. No FDG-PET at baseline and a positive FDG-PET at follow-up: If the positive FDG-PET at follow-up corresponds to a new site of disease confirmed by CT, this is PD.

If the positive FDG-PET at follow-up is not confirmed as a new site of disease on CT, additional follow-up CT scans are needed to determine if there is truly progression occurring at that site (if so, the date of PD will be the date of the initial abnormal FDG-PET scan).

If the positive FDG-PET at follow-up corresponds to a pre-existing site of disease on CT that is not progressing on the basis of the anatomic images, this is not PD.

2.4. Evaluation of best overall response

The best overall response is the best response recorded from the start of the study treatment until the end of treatment taking into account any requirement for confirmation. The subject's best overall response assignment will depend on the findings of both target and non-target disease and will also take into consideration the appearance of new lesions.

2.4.1. Time point response

Table 1 on provides a summary of the overall response status calculation at each time point for subjects who have measurable disease at baseline.

Target lesions	Non-target lesions	New lesions	Overall response
CR	CR	No	CR
CR	Non-CR/non-PD	No	PR
CR	Not evaluated	No	PR
PR	Non-PD or not all evaluated	No	PR
SD	Non-PD or not all evaluated	No	SD
Not all evaluated	Non-PD	No	NE
PD	Any	Yes or No	PD
Any	PD	Yes or No	PD
Any	Any	Yes	PD

CR = complete response, PR = partial response, SD = stable disease, PD = progressive disease, and NE = inevaluable.

2.4.2. Missing assessments and non-evaluable designation

When no imaging/measurement is done at all at a particular time point, the subject is not evaluable (NE) at that time point. If only a subset of lesion measurements are made at an assessment, usually the case is also considered NE at that time point, unless a convincing argument can be made that the contribution of the individual missing lesion(s) would not change the assigned time point response. This would be most likely to happen in the case of PD. For example, if a subject had a baseline sum of 50 mm with 3 measured lesions and at follow-up only two lesions were assessed, but those gave a sum of 80 mm, the subject will have achieved PD status, regardless of the contribution of the missing lesion.

2.4.3. Best overall response: all time points

The best overall response is determined once all the data for the subject is known.

Best response determination in this trial where confirmation of complete or partial response IS NOT required: Best response in these trials is defined as the best response across all time points (for example, a subject who has SD at first assessment, PR at second assessment, and PD on last assessment has a best overall response of PR). When SD is believed to be best response, it must also meet the protocol specified minimum time from baseline. If the minimum time is not met when SD is otherwise the best time point response, the subject's best response depends on the subsequent assessments. For example, a subject who has SD at first assessment, PD at second and does not meet minimum duration for SD, will have a best response of PD. The same subject lost to follow-up after the first SD assessment would be considered non-evaluable.

2.4.4. Special notes on response assessment

When nodal disease is included in the sum of target lesions and the nodes decrease to 'normal' size (< 10 mm), they may still have a measurement reported on scans. This measurement should be recorded even though the nodes are normal in order not to overstate progression

should it be based on increase in size of the nodes. As noted earlier, this means that subjects with CR may not have a total sum of 'zero' on the case report form (CRF).

Subjects with a global deterioration of health status requiring discontinuation of treatment without objective evidence of disease progression at that time should be reported as 'symptomatic deterioration'. Every effort should be made to document objective progression even after discontinuation of treatment. Symptomatic deterioration is not a descriptor of an objective response: it is a reason for stopping study therapy. The objective response status of such subjects is to be determined by evaluation of target and non-target disease as shown in Table 1, Table 2, and Table 3.

In some circumstances it may be difficult to distinguish residual disease from normal tissue. When the evaluation of complete response depends upon this determination, it is recommended that the residual lesion be investigated (fine needle aspirate/biopsy) before assigning a status of complete response. FDG-PET may be used to upgrade a response to a CR in a manner similar to a biopsy in cases where a residual radiographic abnormality is thought to represent fibrosis or scarring. The use of FDG-PET in this circumstance should be prospectively described in the protocol and supported by disease specific medical literature for the indication. However, it must be acknowledged that both approaches may lead to false positive CR due to limitations of FDG-PET and biopsy resolution/sensitivity.

For equivocal findings of progression (eg, very small and uncertain new lesions; cystic changes or necrosis in existing lesions), treatment may continue until the next scheduled assessment. If at the next scheduled assessment, progression is confirmed, the date of progression should be the earlier date when progression was suspected.

13.4. Appendix D. Modified RECIST (mRECIST)¹⁰

FORMULA

Responses are defined as the following (RECIST is listed for comparison):

	RECIST	mRECIST
Complete response	Disappearance of all target lesions	Disappearance of any intratumoral arterial enhancement in all target lesions
Partial response	At least a 30% decrease in the sum of diameters of target lesions, taking as reference the baseline sum of the diameters of target lesions	At least a 30% decrease in the sum of diameters of viable (enhancement in the arterial phase) target lesions, taking as reference the baseline sum of the diameters of target lesions
Stable disease	Any cases that do not qualify for either partial response or progressive disease	Any cases that do not qualify for either partial response or progressive disease
Progressive disease	An increase of at least 20% in the sum of the diameters of target lesions, taking as reference the smallest sum of the diameters of target lesions recorded since treatment started	An increase of at least 20% in the sum of the diameters of viable (enhancing) target lesions, taking as reference the smallest sum of the diameters of viable (enhancing) target lesions recorded since treatment started

<https://www.mdcalc.com/modified-response-evaluation-criteria-solid-tumors-mrecist#evidence>

Modified RECIST criteria were proposed to address scenarios where treatment did not result in overall tumor shrinkage but did cause intratumoral necrosis, reducing viable tumor. Tumor response after ablation will also include assessment by modified RECIST guidelines to incorporate measurements of viable tumor. Similar to RECIST, target lesions must appear suitable for accurate and repeat measurements, and have a diameter of 1 cm or more, while non-target lesions have diameter < 1 cm. At baseline and follow up imaging, measurement of the longest viable tumor diameter should not include any major intervening areas of necrosis. Multiphasic post-contrast imaging will be available; the radiologist will choose the phase of imaging for measurement that best delineates the viable tumor component. If there are multiple intratumoral areas of enhancing viable tumor surrounded by areas of necrosis within the same target lesion, only the longest viable tumor diameter should be captured, again avoiding the

inclusion of any major intervening areas of necrosis. For evaluation by mRECIST, CR is defined by absence of enhanced areas in target lesions; PR and PD as the same degree of decrease and increase as in the RECIST criteria, with sums of diameters of enhanced areas in target lesions rather than sums of diameters of the whole target lesions size; and SD as neither PR or PD.¹¹⁻¹⁶

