1.2. Background

1.2.1. Study Disease

Desmoid tumor is a non-metastasizing but locally aggressive neoplasm that can occur anywhere throughout the body. Desmoids are rare with an estimated incidence in the general population of 2 to 4 per million population per year.² Affected populations can occur in any age group, most commonly seen between the ages of 15 to 60, with a slight preponderance among women than men. Affected locations can include upper and lower extremities, trunk, head and neck region, abdominal wall, and intra-abdominal. The natural history of desmoid is extremely

variable and there are some tumors that spontaneously regress, some that remain stable for years, and some that have unrelenting growth. Tumors that occur intra-abdominally and are associated with familial adenomatous polyposis (FAP) tend to be multi-focal, more aggressive, and potentially fatal. Under histologic exam, desmoid tumors appear as spindle cells in an abundant fibrous stroma with low cellularity, few mitotic figures, and absent necrosis. Staining for nuclear beta-catenin is commonly seen and a fair amount of desmoids have mutations in Catenin Beta 1 (CTNNB1). Other mutations seen are adenomatous polyposis coli (APC) mutations, which are found in FAP patients.

For growing desmoid tumors, options include surgical resection (which can be morbid and has a high recurrence rate), radiation therapy, systemic therapy [such as chemotherapy or vascular endothelial growth factor receptor tyrosine kinase inhibitors (VEGF-TKIs)], and more recently, ablation procedures, such as cryoablation or high intensity focused ultrasound (HIFU).

However, each approach has its pros and cons. For radiation therapy, local control rates are excellent, with approximately 80% at 3 years, however, there are potentially devastating albeit rare long-term side effects such as secondary malignancies.³ For systemic therapy, the time to response is longer (sorafenib trial median of 9 months), and there is associated systemic toxicity. Chemotherapy (doxil, methotrexate/vinblastine) have higher response rates and faster time to response; however, they have more significant side effects than TKIs. For ablation procedures, it may not be technically feasible to totally treat the tumor due to proximity to critical structures such as nerve and skin, there is often a need for multiple treatment sessions. Tumor recurrence or progression is inevitable for tumors that cannot be completely ablated.

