2.3.2.2. Secondary Outcomes

- **Outcome 2 (Secondary) Title:** Clinical Benefit per mRECIST

Description: Clinical benefit (CB) is defined as the number of participants assessed with a complete response (CR), partial response (PR), or stable disease (SD) within 1 year and with no evidence of loss of response nor progression within that year.

Response & progression will be assessed according to the modified Revised Response Evaluation Criteria in Solid Tumors (mRECIST), as follows.

mRECIST:

- CR=Disappearance of intratumoral enhancement
- PR= $\geq 30\%$ decrease in the diameter of target lesion(s)
- PD=An increase of $>20\%$ in the diameter of target lesion.

The outcome is the number of participants alive after 1 year and without PD per mRECIST, a number without dispersion.

Time Frame: 1 year

- **Outcome 3 (Secondary) Title:** Progression-free Survival (PFS)

Description: Progressive-free survival (PFS) is an assessment of the number of participants at a specific time who remain alive and without tumor progression.

Progressive disease (PD) will be assessed according to Revised Response Evaluation Criteria in Solid Tumors (RECIST)v1.1, or, for tumors assessed with MRI enhancement, modified RECIST (mRECIST) defined as follows:

RECIST v1.1:

- PD=20% increase in diameter of target lesion; progression of non-target lesion; or ≥ 1 new lesion(s)

mRECIST:

- PD=An increase of $>20\%$ in the diameter of target lesion.

The outcome is the number of participants alive after 1 year and without PD per RECIST or mRECIST, a number without dispersion.

Time Frame: 1 year

- **Outcome 4 (Secondary) Title:** Objective Response

Description: Objective response (OR) is defined as the number of participants assessed with a complete response (CR) or partial response (PR) within 1 year and with no evidence of loss of response nor progression within that year. Response & progression will be assessed according to the Revised Response Evaluation Criteria in Solid Tumors (RECIST)v1.1, or, for assessed with MRI enhancement, modified RECIST (mRECIST) as follows:

RECIST v1.1:

- CR=Disappearance of all lesions
- PR= $\geq 30\%$ decrease in diameter of target lesions
- Progressive disease (PD)=20% increase in diameter of target lesion; progression of non-target lesion; or ≥ 1 new lesion(s)

mRECIST:

- CR=Disappearance of intratumoral enhancement
- PR= $\geq 30\%$ decrease in the diameter of target lesion(s)
- PD=An increase of $>20\%$ in the diameter of target lesion.

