13.5. Appendix E. Tumor Volume Calculation by MRI

A short-coming of both RECIST and mRECIST is their reliance on measuring single diameters. A more accurate and reproducible approach would utilize both total and viable tumor volumes for comparison of treatment results. For this purpose, T1-weighted fat suppressed post-contrast MR images of the target lesion will be manually segmented on each slice by a radiologist using a free open-source software package (Horos). The total tumor area will be contoured on each slice, as will the total enhancing viable tumor area. The areas of the segmented lesion will be used to calculate the volume of interest for computer-based image analysis by summing areas of the tumor on each slice and multiplying by slice thickness to obtain total tumor volume. For evaluation by MR volumetry, CR is defined by absence of enhanced volume in target lesions; PR and PD as the same degree of decrease and increase as in the RECIST criteria, with volumes of enhanced areas in target lesions rather than sums of diameters of the whole target lesions size; and SD as neither PR or PD.¹⁷

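### For secondary endpoints, the mRECIST and volumetric progression rules ignore new and non-target lesions, and section 2.3.2.2 defines mRECIST response and progression differently from Appendix D

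*Protocol*

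**What the plan says.** The protocol uses three imaging criteria. RECIST v1.1 serves the primary clinical benefit rate (CBR). mRECIST serves a secondary CBR. All three serve PFS, ORR, time to response and duration of response (Synopsis, Secondary Endpoints; section 10.2.2).

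- **Appendix C (RECIST v1.1), 2.3.1.** After the size criterion it adds that "the appearance of one or more new lesions is also considered progression". The time-point table in 2.4.1 lets new or non-target progression override any target response.
- **Appendix D (mRECIST).** Progression is "An increase of at least 20% in the sum of the diameters of viable (enhancing) target lesions", relative to nadir. Stable disease is "Any cases that do not qualify for either partial response or progressive disease". The narrative says the RECIST percentages apply "with sums of diameters of enhanced areas in target lesions rather than sums of diameters of the whole target lesions size". Non-target lesions are defined by size (under 1 cm) but given no progression rule.
- **Appendix E (volumetry).** "CR is defined by absence of enhanced volume in target lesions". Partial response and progression use the RECIST percentages "with volumes of enhanced areas in target lesions rather than sums of diameters of the whole target lesions size". Stable disease is again the remainder.
- **Section 2.3.2.2 (registered secondary outcomes).** mRECIST complete response is loss of enhancement. Partial response is a 30% or greater "decrease in the diameter of target lesion(s"), and progression is an increase of more than 20% in target-lesion diameter; neither mentions enhancement. RECIST progression, listed beside it, includes non-target progression and new lesions. The mRECIST clinical benefit outcome counts those alive at 1 year without mRECIST progression.

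**The concern.** Three faults differ in weight.

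1. mRECIST and volumetric progression depend on target lesions alone. A new desmoid, or growth of one not chosen as a target, then falls into stable disease or better. The situation is possible here: only one mass is ablated (section 5.2), imaging must cover all areas of disease (section 6.2.1), and section 1.2.1 says intra-abdominal tumours associated with familial polyposis "tend to be multi-focal, more aggressive, and potentially fatal".
2. The registered wording keeps enhancement for complete response but drops it for partial response and progression. Appendix D says mRECIST exists for treatment that kills tumour without shrinking it, which is what ablation may do. On whole-lesion diameter that effect is not seen.
3. A lesser fault: the Appendix D partial-response cell compares viable diameter with the baseline sum of target lesions, not of viable target tumour.

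The mRECIST CBR is the first secondary endpoint. Section 10.4.3 says the 50% historical rate was itself determined by mRECIST, so this result is the closest in criterion to the comparator. If the definition is settled only after images are read, the choice may be influenced by the data.

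**Working it through.** The plan states no figure that depends on these definitions, so the check sets the rules side by side and applies them.

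**Step 1. What counts as progression.**

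| Criterion | Target growth | Non-target progression | New lesion |
|---|---|---|---|
| RECIST v1.1 (Appendix C; 2.3.2.1) | yes | yes | yes |
| mRECIST (Appendix D) | at least 20%, enhancing diameter | not stated | not stated |
| mRECIST (2.3.2.2) | more than 20%, diameter | not stated | not stated |
| Volumetry (Appendix E) | RECIST percentage, enhancing volume | not stated | not stated |

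No sentence carries the RECIST rule for new or non-target lesions over to the other two criteria.

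**Step 2. Illustrative lesions.** Diameters are assumed, in mm. Response = (baseline − now)/baseline, at least 30%. Progression = (now − nadir)/nadir, at least 20% (Appendix D) or more than 20% (2.3.2.2).

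- **A.** Whole lesion 100 → 100, viable 100 → 60. Appendix D: (100 − 60)/100 = 40%, partial response. Section 2.3.2.2: 0%, stable.
- **B.** Whole lesion 100 throughout, viable 100 → 50 → 65. Appendix D: (65 − 50)/50 = 30%, progression. Section 2.3.2.2: 0%, stable.
- **C.** Whole lesion 100 throughout, viable 100 → 95, plus a new desmoid. Appendix D: 5% decrease, stable. Section 2.3.2.2: stable. RECIST v1.1: progression.
- **D.** Whole and viable both 100 → 120. Increase is exactly 20%. Appendix D: progression. Section 2.3.2.2: stable.
- **E.** Whole lesion 100, viable 68, both unchanged. Appendix D table cell read literally: (100 − 68)/100 = 32%, partial response. Appendix D narrative: (68 − 68)/68 = 0%, stable.

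C is the first fault, A, B and D the second, E the third. A hides a response and B hides a progression, so the second fault has no fixed direction.

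**Step 3. Size for the mRECIST CBR.** With the 20 evaluable subjects of section 10.4.1 all assessed by mRECIST, one subject is 1/20 = 5 percentage points. Suppose 16 of 20 have no mRECIST progression as the rule stands (0.8 × 20 = 16, the planning alternative), and k of those 16 have a new lesion as their only event. Counting it as progression gives (16 − k)/20:

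| k | 0 | 1 | 2 | 3 | 4 |
|---|---|---|---|---|---|
| mRECIST CBR | 80% | 75% | 70% | 65% | 60% |

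The documents give no basis for choosing k.

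**Step 4. Reach.** With no volumetric CBR planned, the volumetric gap affects PFS and duration of response through missed progression. It affects ORR and time to response where a target response coincides with a new lesion.

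**The case against.** The strongest defence of the first fault is that Appendix D shows only how target measurement is modified and assumes the RECIST framework for everything else. Its RECIST column also omits new lesions, although Appendix C includes them, and the appendix defines non-target lesions, which would be idle if they played no part. That makes an innocent intention plausible. It does not settle the text: section 2.3.2.2 lists new lesions under RECIST and leaves them out under mRECIST in the same outcome.

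On the second fault, section 2.3.2 is a registry summary that shortens RECIST as well, and section 10.2.2.1 sends the mRECIST analysis to Appendix D. So the analysis probably follows the appendix. The contradiction in the published outcome remains.

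On the third, the Appendix D narrative measures viable diameter at baseline and follow-up, which largely answers the table cell. The 68 mm in case E is invented.

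The frequency objection stands in full. Desmoid does not metastasise (section 1.2.1), and the eligibility of multifocal disease is inferred from the criteria not excluding it. A subject with early RECIST progression may stop treatment and, under section 10.2.1.3, may not be evaluable at 1 year.

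A reader might infer that the primary result is inflated, or that registered mRECIST simply duplicates RECIST. Neither is supported. The primary CBR uses RECIST v1.1, where a new lesion is progression. Registered mRECIST still differs from RECIST in its complete-response rule and in lacking new and non-target lesions.

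**Conclusion.** The point holds for secondary endpoints and should be fixed before endpoint images are read. As written, mRECIST and volumetric progression omit new and non-target lesions. This favours the treatment in mRECIST CBR and can do so in mRECIST and volumetric PFS, ORR, time to response and duration of response. The size is 5 points of mRECIST CBR per affected subject, assuming 20 assessed; the number affected is unknown and could be zero. Section 2.3.2.2 also contradicts Appendix D on what is measured and on the progression threshold, which can hide responses and progressions alike. The partial-response cell is a wording correction: a reader might infer a stream of false partial responses from it, but the narrative below the table points to the right reference. The primary CBR and its decision rule are untouched.

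**What to change.** - In Appendix D, Appendix E and the mRECIST entries of section 2.3.2.2, state that unequivocal non-target progression or any new lesion is progression, in the terms of Appendix C.
- In section 2.3.2.2, restate mRECIST partial response and progression as change in the summed diameters of enhancing target tumour: at least 30% down from baseline, and at least 20% up from nadir.
- In the Appendix D partial-response cell, make the reference the baseline sum of viable (enhancing) diameters.

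The cost is text in two appendices and the registered outcome wording, with no new scans or readers. The mRECIST CBR, and mRECIST and volumetric PFS and ORR, may come out slightly less favourable. The edits concern endpoint classification only.
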